### **Creatinine Clearance**

If the participant is using Truvada®, and the creatinine clearance is  $<60\text{mL/min}$ , study product should be held, and the test should be repeated as soon as possible (at most within 1 week of the receipt of the results). If a level of  $<60\text{mL/min}$  is confirmed with retesting, Truvada® study product should be permanently discontinued in consultation with the CMC. If Descovy® is available, the participant should be switched to this medication. If retesting cannot be completed within one week, all attempts should be made by the site to contact the participant for retesting within three additional working days. A participant who fails to undergo confirmatory testing within one week plus three additional working days will require CMC consultation regarding further product management.

If re-testing yields a result  $\geq 60\text{mL/min}$ , the IoR/designee must consult the CMC for further guidance on resuming product use, continuing the hold temporarily, or progressing to permanent discontinuation.

If the participant is using Descovy®, and the creatinine clearance is <30mL/min, study product should be held, and the test should be repeated as soon as possible (at most within 1 week of the receipt of the results). If a level of <30mL/min is confirmed with retesting, Descovy® should be permanently discontinued in consultation with the CMC. If retesting cannot be completed within one week, all attempts should be made by the site to contact the participant for retesting within three additional working days. A participant who fails to undergo confirmatory testing within one week plus three additional working days will require CMC consultation regarding further product management.

If re-testing yields a result  $\geq 30$ mL/min, the IoR/designee must consult the CMC for further guidance on resuming product use, continuing the hold temporarily, or progressing to permanent discontinuation.

If clinical suspicion for renal failure exists, local medical resources with clinical expertise in renal failure must be engaged to the extent available.

NOTE: Adverse events related to creatinine clearance should be based on the assessment of BOTH the absolute creatinine clearance AND the change in creatinine clearance from baseline (Screening Visit). When gradable, only the higher grade of these two assessments should be entered on the Adverse Event e-CRF.

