### **4.1 Inclusion Criteria**

TGW (assigned male at birth, trans-feminine spectrum – as defined in the SSP Manual – by self-report) who meet all of the following criteria are eligible for inclusion in this study.

1. Eighteen years or older at the time of screening.
2. Willing and able to provide informed consent for the study.
3. Interest in PrEP – as defined in the SSP Manual.

4. Non-reactive HIV test results at Screening and Enrollment.
5. Available to return for all study visits and within site catchment area, as defined per site's Standard Operating Procedures (SOP).
6. At risk for sexually acquiring HIV infection based on self-report of at least one of the following:
  - a) Any anal or vaginal sex with one or more serodiscordant or HIV-unknown serostatus sexual partners in the previous 3 months, regardless of condom use.
  - b) Anal or vaginal sex in exchange for money, food, shelter, or other goods or favors in the previous 3 months.
  - c) History of STI(s) in the past 6 months.
7. Willing to undergo all required study procedures.
8. General good health, as evidenced by the following laboratory values:
  - a) Calculated creatinine clearance  $\geq$  60 mL/minute using the Cockcroft-Gault equation.
  - b) Alanine aminotransferase (ALT) and aspartate aminotransferase (AST)  $<$  2.5 times the upper limit of normal (ULN.)
  - c) HBV surface antigen (HBsAg) negative.

*Note: Otherwise eligible participants with laboratory results outside the above-mentioned values, with the exception of those with reactive HIV test, can be re-tested during the screening window. Participants with reactive HIV tests will not be able to rescreen.*

*Note: Participants who practice receptive vaginal sex cannot be provided Descovy® as it is not approved for this indication.*

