### **5.2 Study Product Administration**

#### PrEP

FTC/TDF 200mg/300mg (Truvada®) or FTC/TAF 200mg/25mg (Descovy®) will be taken as one tablet orally once daily with or without food during the 18 months of study participation.

Participants do not have to accept PrEP to be eligible to participate in the study. A participant can decide to initiate PrEP administration at any time after enrollment up until, and including, the Week 39 study visit. Once initiated, the study participant may also decide to discontinue taking PrEP at any time during the 18 months of study participation. A participant can reinitiate PrEP after discontinuation up to, and including, Week 65 of study participation. If a participant requests to reinitiate PrEP at site after discontinuation and had originally initiated PrEP use at site by Week 39 of study participation, the participant is eligible to receive PrEP provided by the study at the site. If a participant has not been provided PrEP at the site by Week 39 and decides to

initiate PrEP after the Week 39 study visit, PrEP will not be provided at the study site; rather the participant will be linked to local PrEP services.

For participants in the U.S., a choice of either Descovy® (FTC/TAF) or Truvada® (FTC/TDF) will be offered at the enrollment visit. Participants may choose to switch PrEP study agents during follow-up. Site staff must document in eCRFs which PrEP study product a participant initiates and if study product is switched during follow-up.

For participants enrolled at the site in Brazil, only Truvada® (FTC/TDF) will be offered as PrEP study product as noted in Section 5.1.

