### **6.4.1 Follow Up Procedures for Participants Who Discontinue Study Products**

A participant may discontinue use of PrEP and/or hormonal therapy and remain on study. Product may be held in response to a clinical event or participant-initiated decision. Discontinuation is defined as not using study product for 30 or more days, independently of the rational for study product discontinuation. If this occurs, study visits continue according to the Schedule of Events (SOE) found in Appendix Ia, with the exceptions noted in Tables 4 and 5.

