## APPENDIX II: TOXICITY MANAGEMENT

### A. General Guidance:

Guidelines for clinical management and temporary product hold/permanent discontinuation of study product are outlined in this section. In general, the IoR/designee has the discretion to hold study product temporarily at any time if she/he feels that continued product use would be harmful to the participant or interfere with treatment deemed clinically necessary. Unless otherwise specified below, the IoR/designee should immediately consult the CMC for further guidance on resuming study product, continuing the hold temporarily, or progressing to permanent discontinuation of study product. The IoR/designee will document all temporary product holds and permanent discontinuations on applicable eCRFs.

*Management of toxicities under Section A apply to all study products – PrEP and GAHT.*

#### Grade 1 or 2

In general, a participant who develops a Grade 1 or 2 AE, regardless of relationship to study product may continue product use. If the IoR opts to temporarily hold study product, the CMC must be notified.

#### Grade 3

Participants who develop a Grade 3 AE that is judged by the IoR/designee to be unrelated to study product may continue product use but must immediately consult the CMC regarding further management.

For participants who develop a Grade 3 AE that is judged by the IoR/designee to be related to product, study product must be temporarily held until the CMC can be consulted regarding potential resumption or other further management.

If study product is resumed and the same Grade 3 AE recurs at any time during the study, the IoR must consult the CMC for guidance on product use and clinical management. If the Grade 3 AE is deemed related to study product, study product must be temporarily held until the CMC can be consulted regarding permanent discontinuation or other further management.

#### Grade 4

A participant who develops a Grade 4 AE, regardless of relationship to study product, will have the study product temporarily held. The IoR/designee must consult the CMC and continue the temporary product hold until a recommendation is obtained from the CMC. If, in consultation with the CMC, product use is resumed, and the same AE recurs at Grade 4 level at any time during the study, study product must then be permanently discontinued.

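### Appendix II B directs a switch from Truvada to Descovy with no exception for participants whom the Section 4.1 note bars from Descovy

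*Combined protocol and SAP*

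**What the plan says.** Three parts of the protocol bear on this.

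- **Section 4.1, note under the inclusion criteria:** "Participants who practice receptive vaginal sex cannot be provided Descovy® as it is not approved for this indication". This is not an eligibility criterion. Such participants may enroll, and the note limits which agent they may be given.
- **Appendix II B, Creatinine Clearance:** for a Truvada user whose clearance is below 60 mL/min on retest, "Truvada® study product should be permanently discontinued in consultation with the CMC". The next sentence reads "If Descovy® is available, the participant should be switched to this medication".
- **Section 5.2, PrEP:** U.S. sites stock both agents ("For participants in the U.S., a choice of either Descovy® (FTC/TAF) or Truvada® (FTC/TDF) will be offered at the enrollment visit"), whereas "For participants enrolled at the site in Brazil, only Truvada® (FTC/TDF) will be offered as PrEP study product".

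In the documents provided, the restriction on Descovy appears only in the Section 4.1 note. The regimen table in Section 5.1, the initiation and re-initiation procedures in Section 6.4.2, and Appendix II do not repeat it or refer to it.

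**The concern.** A clinician acting on an abnormal creatinine result works from the toxicity appendix, perhaps months after the eligibility criteria were last consulted. Read on its own, the appendix tells that clinician to give Descovy to anyone who must come off Truvada, if the site has it. For a participant who practices receptive vaginal sex, following that sentence means departing from Section 4.1, and following Section 4.1 means departing from the appendix.

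The rule also falls directly on the restricted group. Under the Section 4.1 note, a U.S. participant in that group who takes study PrEP has to be on Truvada, so she is always subject to the 60 mL/min rule. Nothing later in the appendix would stop the switch: Descovy's own hold threshold is 30 mL/min, so a clearance between 30 and 60 passes it.

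What is at stake is the internal consistency of a rule that ties an agent to its approved indication.

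**Working it through.** The protocol states no figure on this point, so there is none to reproduce. The check is a comparison of texts, followed by a rough bound on how many participants could meet the conflict.

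**Comparison of texts**

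1. *Who is restricted.* Section 4.1: participants who practice receptive vaginal sex. The prohibition is categorical.
2. *Who is directed to Descovy.* Appendix II B: every participant on Truvada with a confirmed clearance below 60 mL/min, where Descovy is available. Sexual practice is not mentioned.
3. *Overlap.* Participants in both sets, at a site that has Descovy. Section 5.2 makes those the U.S. sites.
4. *Whether another text resolves the overlap.* Section 6.4.2 has a general proviso about contraindications, but it concerns starting and restarting PrEP, not a switch of agent. Appendix II A says "Unless otherwise specified below, the IoR/designee should immediately consult the CMC for further guidance on resuming study product". That default yields to specific instructions further down, and the switch sentence is one. The CMC wording in Appendix II B belongs to the sentence that stops Truvada; the switch is a separate sentence.

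So for the overlap, the literal instruction in Appendix II B and the prohibition in Section 4.1 cannot both be followed.

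**Bound on the number affected**

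Inputs from the protocol: about 310 participants (Section 4.0); four U.S. sites and one in Brazil (Schema); a higher enrollment target for Brazil (Section 8.4); clearance of at least 60 mL/min at entry (Section 4.1, criterion 8a).

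- Equal split: 310 / 5 = 62 per site. With a higher target for Brazil, the U.S. total is below 310 − 62 = 248.

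Assumptions, none of them in the documents:

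- 2% to 10% of U.S. participants practice receptive vaginal sex;
- 50% to 100% of these take study PrEP (Truvada, by the Section 4.1 note);
- 0.5% to 5% of those have a confirmed clearance below 60 mL/min during follow-up.

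Expected number reaching the conflict = 248 × (product of the three proportions). Chance of at least one = 1 − (1 − product)^248.

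| | Product | Expected number | Chance of at least one |
|---|---|---|---|
| All low | 0.02 × 0.5 × 0.005 = 0.00005 | 248 × 0.00005 = 0.012 | 1 − 0.99995^248 = 0.012 |
| All high | 0.10 × 1.0 × 0.05 = 0.005 | 248 × 0.005 = 1.24 | 1 − 0.995^248 = 0.712 |

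The upper row puts all three high assumptions on top of a ceiling of 248. Both rows count participants who reach the sentence, not participants wrongly given Descovy, who would be fewer.

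**The case against.** The best defense is that Section 4.1 already governs. Its wording is an absolute bar on providing the drug, while Appendix II B says only what should happen; a categorical bar ordinarily limits a general instruction, so nothing more than a cross-reference is missing. Several safeguards also sit around this step. Truvada is stopped in consultation with the CMC, whose remit in Section 8.9 covers toxicity management and permanent discontinuation. Section 5.5 requires a written prescription when either agent is started. Section 5.8 requires current Package Inserts to be at hand. Section 11.3 says that the SSP Manual, which was not among the documents, covers adverse event management and dispensing, and it may repeat the restriction.

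Much of this stands. A careful reader may well let Section 4.1 prevail, and the safeguards make a wrong dispensation unlikely. They do not remove the conflict. No text says that Section 4.1 limits Appendix II, and the protocol should be consistent without relying on a manual or on someone catching the error.

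A reader might infer more than the documents support:

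- *That these participants are left with no instruction once Truvada stops.* They are not. Section 6.4.1 says "A participant may discontinue use of PrEP and/or hormonal therapy and remain on study", and Table 4 lists which procedures then cease.
- *That Section 5.2 is equally in error, because its enrollment offer and its statement that "Participants may choose to switch PrEP study agents during follow-up" omit the restriction.* Those sentences are permissive, and it is reasonable to read them as limited by the bar in Section 4.1. A cross-reference there would be editorial tidying.
- *That the gap threatens the adherence comparison or reduces protection against HIV.* Nothing in the documents supports either. Section 8.6.1 classifies adherence by drug levels under either regimen, and the Section 4.1 note speaks only of the approved indication.

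**Conclusion.** The point holds as a minor error of wording. Appendix II B, as written, directs a switch to Descovy that the Section 4.1 note prohibits for participants who practice receptive vaginal sex. It applies at U.S. sites only and probably touches about one participant or none; the range of 0.01 to 1.2 expected rests wholly on assumed proportions and on a U.S. enrollment ceiling of 248. Sample size, power and the primary analysis are unaffected. It merits correction because a participant-protection rule should not tell a site to do what the protocol forbids. Confidence is medium, mainly because the SSP Manual was not available.

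**What to change.** Amend the switch sentence in Appendix II B to this effect: *where Descovy is available and the participant does not practice receptive vaginal sex (see the note in Section 4.1), switch to Descovy; otherwise PrEP remains discontinued, follow-up continues under Section 6.4.1, and the CMC is consulted on further PrEP management.*

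The edit is one sentence and changes no visit, data item or analysis. It is not free. Section 11.5 requires prior written approval from the Protocol Chair and the DAIDS Medical Officer, and then approval by the IRBs/ECs and the RSC; Section 11.1 adds a registration packet for a full amendment. That is out of proportion for this change alone, so it should go in with the next protocol amendment. A reference to the Section 4.1 note in Section 5.2 could be added at the same time, as an option.

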#### 6.4.2 Procedures for Participants who Initiate or Re-initiate Study Products

There are some situations when a participant may initiate or re-initiate product use during follow-up. This includes product being held due to a clinical event or because a participant declines either PrEP or GAHT during follow-up. Re-initiation is defined as restarting study product use after 30 or more days off study product.

Participants who decline PrEP can begin (or reinitiate) PrEP at any time up to and including their Week 39 visit unless contraindicated. At the visit when PrEP is to be initiated or reinitiated, the following procedures should be conducted, and **results should be available prior to PrEP dispensation:**

- Creatinine clearance
- HIV testing
- Fasting lipid profile (for participant reinitiating PrEP, lipid profile is not required if done within six months of product re-initiation)

Participants may begin co-located GAHT any time after enrollment (Immediate Intervention Arm) or after the 6-month visit (Deferred Intervention Arm) up to and including the Week 39 visit unless contraindicated. At the visit when co-located GAHT is to be initiated or reinitiated, the following procedures should be conducted, and **results should be available prior to GAHT dispensation:**

- Estradiol and total testosterone testing

If either product was held due to a clinical event, sites need to assess the event and confirm resolution. This may be done by clinical assessment, medical history, and/or laboratory assessment.

The CMC may be consulted for additional guidance prior to initiation/re-initiation of study product(s).

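### The switch from Truvada to Descovy after a confirmed creatinine clearance below 60 mL/min has no lower limit, so below 30 mL/min it conflicts with the protocol's own rule for stopping Descovy

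*Combined protocol and SAP*

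**What the plan says.** The rules are in Appendix II, Part B, under Creatinine Clearance.

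- **On Truvada.** A value below 60 mL/min leads to a hold and a retest. If it is confirmed, "Truvada® study product should be permanently discontinued in consultation with the CMC". The next sentence is "If Descovy® is available, the participant should be switched to this medication".
- **On Descovy.** A value below 30 mL/min leads to a hold and a retest. Then: "If a level of <30mL/min is confirmed with retesting, Descovy® should be permanently discontinued in consultation with the CMC".
- **Both agents.** If renal failure is clinically suspected, local renal expertise must be brought in as far as it is available.

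Appendix II, Part A covers all study products. By default it sends decisions after a hold to the CMC: "Unless otherwise specified below, the IoR/designee should immediately consult the CMC for further guidance on resuming study product". It also lets the investigator hold product at any time if continued use would be harmful.

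Section 5.2 limits where the switch can happen: "For participants enrolled at the site in Brazil, only Truvada® (FTC/TDF) will be offered as PrEP study product". At U.S. sites both agents are offered. A note in Section 4.1 bars Descovy for participants who practise receptive vaginal sex.

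**The concern.** The subsection is written as a numeric algorithm, with drug-specific thresholds, retest windows and actions. A reader would expect it to give one consistent action for every confirmed value. It does not, because a value below 30 mL/min is also a value below 60 mL/min. A site following the Truvada paragraph literally would move a participant with a confirmed value of, say, 25 mL/min to Descovy. The protocol's own Descovy paragraph makes that value a reason for permanent discontinuation.

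At stake is the safety of the few participants with the most severe renal decline. Section 9.3.2 lists new or worsening kidney damage as a rare but serious risk of FTC/TAF. PrEP is prescribed to last through the next study visit (Section 5.5), and scheduled creatinine clearance tests are quarterly (Appendix Ia). Endpoints, sample size and error rates are not touched.

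**Working it through.** There is no plan figure to reproduce. The check sets the rules side by side, looks for a floor elsewhere, and works out how large a fall the case requires.

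**1. Action by confirmed value, for a U.S. participant on Truvada**

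| Retest result (mL/min) | Truvada paragraph | Descovy paragraph | Consistent? |
|---|---|---|---|
| 60 or above | Consult the CMC on resuming, holding or stopping | Not engaged | Yes |
| 30 to below 60 | Stop Truvada, switch to Descovy | Descovy may be used | Yes |
| Below 30 | Stop Truvada, switch to Descovy | Hold; stop permanently if confirmed | **No** |

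The Descovy paragraph is worded for someone already taking Descovy. It does not itself forbid starting the drug.

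**2. Is a floor set anywhere else?**

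- Section 4.1 requires at least 60 mL/min, but only for entry. Its note bars Descovy for receptive vaginal sex and gives no renal bar.
- Section 5.2 lets U.S. participants change agents during follow-up and names no renal limit.
- Section 6.4.2 requires a creatinine clearance result before PrEP is started or restarted, but gives no cut-off. It defines re-initiation as a restart after 30 or more days off product, which a prompt switch may not meet.
- Appendix II, Part A works by adverse event grade and names no creatinine clearance value.

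So no floor is stated.

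**3. Where does CMC consultation attach?** It is written into the sentence that stops Truvada. The switch is a separate sentence without it. The general CMC default in Part A gives way where something else is specified below it, and the switch is specified below it.

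**4. How large a fall is needed?** From an entry value b, reaching a value below 30 mL/min needs a proportional fall of more than 1 − 30/b.

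- b = 60 (the entry minimum, Section 4.1): 1 − 30/60 = 50.0%
- b = 90 (illustrative assumption): 1 − 30/90 = 66.7%
- b = 120 (illustrative assumption): 1 − 30/120 = 75.0%

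The documents give no incidence of such falls, so no count of affected participants is offered.

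**The case against.** The strongest reply is that the subsection should be read as a whole. Anyone moved to Descovy below 30 mL/min would at once meet the Descovy hold a few lines further on. Stopping one agent and starting the other is a single management step, already taken with the CMC, and Section 8.9 gives the CMC toxicity management and discontinuations as its business. The switch sentence also cannot be a complete list of conditions, since the Section 4.1 bar for receptive vaginal sex applies without being repeated there.

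Other safeguards add to this:

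- Grade 4 events: "A participant who develops a Grade 4 AE, regardless of relationship to study product, will have the study product temporarily held". The hold lasts until the CMC makes a recommendation. This rule covers all study products and does not carry the exception attached to the general default.
- Grade 3 events judged "to be related to product, study product must be temporarily held until the CMC can be consulted regarding potential resumption". Unrelated Grade 3 events also require immediate CMC consultation.
- Section 6.4.2: "If either product was held due to a clinical event, sites need to assess the event and confirm resolution".
- The investigator's discretion to hold, and the duty to engage renal expertise when renal failure is suspected.

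Much of this stands. The safeguards make it likely that the case would be caught. The point about Section 4.1 also matters for the fix, because a replacement sentence conditioned only on creatinine clearance and availability would, read literally, still direct a switch for participants whom that note bars.

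It does not remove the conflict. A hold that takes effect as soon as the drug is started shows that the two instructions contradict each other, and the text does not say which prevails. The grade-based holds depend on a grading table (Section 7.5) that is not among the documents, so the grade of a value below 30 mL/min cannot be asserted either way. The SSP Manual, also not supplied, may state a limit. If it does, the protocol sentence should match it.

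**Conclusion.** The concern holds as a safety-wording conflict. For a confirmed creatinine clearance below 30 mL/min on Truvada, the protocol directs a switch to an agent that the same subsection stops permanently at that value. The rule is sound from 30 to below 60 mL/min and needs no change there.

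It is a minor point: rare, limited to U.S. Truvada users (and, if the Section 4.1 note is carried over, to those not barred from Descovy), and without effect on the trial's statistical properties. It is still worth correcting, because what is written gives the wrong action in that range, which is more than a missing detail.

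A reader might infer that participants with severe renal decline would in practice be put on Descovy unchecked, or that harm is likely. The documents do not support that. Truvada is already on hold by then, the CMC is consulted on stopping it, and several further safeguards apply. Nor do they support assigning a particular grade to a value below 30 mL/min.

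The conclusion rests on a literal reading of the switch sentence and on the absence of a floor in the documents supplied.

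**What to change.** Reword the switch sentence in Appendix II, Part B along these lines:

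> Switch to Descovy only if the confirmed creatinine clearance is ≥30 and <60 mL/min, Descovy is available, and the participant is not otherwise barred from it (e.g., receptive vaginal sex, Section 4.1). If the confirmed value is <30 mL/min, do not start Descovy; the CMC must be consulted on further PrEP management.

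The 30 mL/min limit is the protocol's own Descovy stopping value. Sending lower values to the CMC leaves room to act if renal function recovers.

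The cost is one clause, with no new visit, test or procedure. Section 11.5 requires IRB/EC and Regulatory Support Center approval before an amendment is implemented, so the change is best bundled with the next amendment. Until then, it can be issued to sites as a clarification from the CMC or in the SSP Manual, after checking whether that manual already states a limit.
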